7.2 Laboratory Procedures/Evaluations

For each participant, approximately 5 tablespoons (75 cc) of blood will be collected in red (no anticoagulant) top, lavender (EDTA anticoagulant) top, green (heparin) and blue (sodium citrate anticoagulant) top tubes. Approximately 3 tablespoons (40 cc) of blood will be used for the different measurements of markers of inflammation and immune activation, and approximately 2 tablespoons (30 cc) of blood will be used to purify cells, RNA and DNA and then stored in -80C/liquid nitrogen for functional profiling. We will perform flow cytometry, ELISA, Treg suppression assays and RNA seq to determine changes in adaptive immune response. None of the above mentioned tests are standard of care. All of the above are necessary for the study to determine if oral butyrate induces a regulatory adaptive immune response in patients.

The drawing of a maximum of 5 tablespoons (75 cc) of blood is justified by the need for the above referenced tests, measurements, and purification and to ensure that enough PBMCs, RNA and serum/plasma are present. These tubes may be drawn at the time of the standard of care blood draws for routine patient care monitoring. This amount of blood is medically safe to draw. The physician will always ensure the safety of drawing this volume of blood.

7.2.1 Specimen Preparation, Handling, and Storage

Blood Collection

Samples will be collected by the NYU study staff or participant's physician or NYU laboratory. Samples will be processed for analysis as described in this protocol. Serum and plasma will be obtained from centrifuged samples of blood and stored for assays of protein levels and other mediators. In addition, peripheral blood cells may be collected, processed, and stored for analysis as well. Samples will be stored at the [name] research laboratory at the NYU Orthopedic Hospital (16th floor) in the dedicated - 80°C freezer space in sterile plastic tubes and storage containers.

Stool and urine Collection

Stool and urine will be collected at the clinic visit or at participant's home as per participant preference. A stool and urine sample will be collected in the stool/urine sample collection kit and immediately placed on freezer packs and either shipped directly overnight to [name] lab, or if collected at clinic visit, will be directly transported to -80C freezer in [name] lab within 4 hours.

Back-Up Storage

All freezers are connected to a back-up generator in the chance that there is an adverse event. All freezers are also connected to the LPRO system, a 24-hour daily maintenance system that monitors temperature and overall status of freezer.

All samples will be taken directly from subjects and no samples will be collected from Pathology.

Vial Labeling

Blood samples will be first collected into tubes labeled with donor's unique Study identification number, date of collection, and sample type. All samples will have freezer safe labels.

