2.4 Potential Risks & Benefits

2.4.1 Known Potential Risks

Risk of study supplement

Butyrate is a normal SCFA fermentation byproduct of our commensal gut microbiota. As such, no risks are expected other than those derived from ingestion of concentrated fatty acids, namely gastrointestinal intolerance (including pain and bloating) and (possibly) diarrhea. Subjects who experience any of these symptoms will be informed to contact their study doctor immediately at the telephone number provided by the PI.

The study team will work to minimize risks by monitoring subject experiences through the study and monitoring the withdrawal of subjects who experience certain risks or severe symptoms. This monitoring will be in the form of discussing with patients during their study visits and tracking of adverse events on case report forms and will be discussed with DSMB as required. There will not be no special monitoring in this case as this is a normal byproduct of gut microbiota and no serious risks are expected from the supplement.

Risks of all study related procedures

Blood draw: Possible side effects from drawing blood include: faintness, inflammation of the vein, pain, bruising, or bleeding at the site of puncture. There is also a slight possibility of infection.

Stool/Urine Sample Collection:

Potential contamination of surfaces or other people is the major risk of urine and stool collection procedure, which may transmit infectious diseases to animals and individuals.

Physical Examination

The physical examination will be performed by a qualified study physician as part of routine care. Minor discomfort may occur.

Loss of privacy and confidentiality: As with participation in any research study, there is always a risk that confidential or private information can be compromised. To minimize this risk, the study team will de-identify patient samples and replace identifying information, such as patient's name, with a bar code label that will not be associated with any date or identifiable information to the patient (for example birthday or street address). Samples will be stored in the PIs lab. Only [name] and his research team will have access to them.

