4.2.2 Secondary Study Endpoints

We will determine changes in serum and fecal SCFA concentration over time to ensure that oral SCFA supplementation is localizing to the colon and/or peripheral circulation.

We will measure changes in adaptive immune response by flow cytometry, ELISA, T reg suppression assays and RNA-seq, over time with oral supplementation of SCFA with the hypothesis that oral SCFA supplementation will increase Treg and B regulatory cell responses over time.

We will measure changes in cytokine production over time with oral supplementation of SCFA with the hypothesis that oral SCFA supplementation will increase regulatory cytokine responses and decrease inflammatory cytokine responses.

Contingent upon observed changes in microbiome and/or changes in adaptive T and B cell populations, measurements of inflammatory transcripts may be performed on stored frozen PBMCs by measuring cell messenger RNA levels.

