When a participant consents to this study, his/her name, address, phone numbers, DOB, and copies of medical records will be collected and kept with the informed consent. At this time, he/she will be assigned a unique study identification number. All subsequent data analysis, specimen recording, and samples will be encoded with this identification number, only and the date of collection. No personal identifiers will be displayed. The principal investigator/project administrator will keep the original, signed informed consents in a locked cabinet in a locked office together with records of specimens donated and medical record copies secured for review. Information with participant names will not be used in any publications resulting from this investigation. The PI will retain the participant contact information until the conclusion of the study.

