11.4 Stored Specimens

All coded samples collected for the study, along with de-identified medical information, may continue to be used and stored under the conditions described in this protocol indefinitely unless subjects request, in writing, for samples to be destroyed.

The reasons for this is that if immunological and/or microbiological markers of interest are identified during this exploratory study, stored samples may be used for further analysis. Any future analysis that is not related to the current protocol will be submitted as a modification to the IRB or under a new study.

All samples will be taken directly from subjects and stored as described in section 7.2.1. Samples will be coded and only the NYU PI, Co-PI, and study coordinators will have access to the linking key between subject ID and subject identity. The PI, Co-PI, and research coordinators will have access to the banked samples.

12 Data Handling and Record Keeping

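### Samples and analysis data are coded by study ID and collection date, and nothing in the plan masks the readers of the Treg assays to visit or group

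*Combined protocol and SAP*

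**What the plan says.** Three sections describe how samples are identified.

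- Section 7.2.1, on vial labelling: "Blood samples will be first collected into tubes labeled with donor's unique Study identification number, date of collection, and sample type". Visit number and group are not listed.
- Section 5.5.2: "All subsequent data analysis, specimen recording, and samples will be encoded with this identification number, only and the date of collection". The dated code is thus not confined to the collection tube.
- Section 2.4.1, under loss of privacy and confidentiality, promises "a bar code label that will not be associated with any date or identifiable information to the patient", with birthday and street address as examples.

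On the assays, section 7.2 says "We will perform flow cytometry, ELISA, Treg suppression assays and RNA seq to determine changes in adaptive immune response". Section 4.2.2 lists the adaptive immune response as a secondary endpoint "with the hypothesis that oral SCFA supplementation will increase Treg and B regulatory cell responses over time". Change in the peripheral Treg population is the first secondary objective in section 3.2, and the Protocol Summary names Treg among the important secondary endpoints.

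On access, section 11.3.1 lets investigators reach both samples and data and says that storage codes are assigned by the investigators. Section 11.4 adds that "only the NYU PI, Co-PI, and study coordinators will have access to the linking key between subject ID and subject identity". Section 6.1 makes the study open label without placebo. No section says who reads the immune assays, in what order or batches, with what gating rule, or with what knowledge of visit or group.

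**The concern.** Treatment is open label by choice, but the immune endpoints are read in a laboratory, where masking is still possible. Gating a flow-cytometry file and setting up or reading a suppression assay leave room for judgement, and the protocol fixes no gating rule. The team also has a prior expectation: 4.2.2 states the direction, and 2.2.1 reports unpublished Treg changes in its own laboratory after butyrate.

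The Treg result is the link between a microbiome change and the regulatory response in the study hypothesis. Under 4.2.2, observed T- and B-cell changes may also trigger further transcript work. The contrast is before versus after within a person. A tendency to read later samples higher would look the same as an SCFA effect, and no masked comparator would expose it. The group not taking SCFA is not randomised, is no better masked, and has an exploratory role under 9.1.

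**Working it through.** The point rests mainly on reading sections together. The arithmetic only shows what is and is not touched.

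**1. Can a reader order the samples?** Inputs: the label in 7.2.1 and the visit windows in 7.3. Visit 1 falls on days -15 to 0. Visit 2 is 30 ± 15 days, so no earlier than day 30 - 15 = 15. Baseline always comes before visit 2. Two tubes with one ID and two dates can be ordered in time without error.

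**2. Does the order reveal SCFA use?** Not by itself. Participants who decline SCFA (up to 30, per the Protocol Summary) are sampled on the same schedule, and the label names no group. The reader also needs to know that the participant took the supplement. No section withholds this, and 11.3.1 gives investigators both samples and data.

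**3. Do the label statements agree?** Read literally, 2.4.1 (no date) conflicts with 5.5.2 and 7.2.1 (date of collection). In context 2.4.1 is about privacy, and its examples suggest that identifying dates are meant. The wording needs reconciling, but 2.4.1 is not a masking rule.

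**4. Is the stated sample size affected?** Sections 9.1 and 9.2 give 23 participants at d = 0.63 and 25 at d = 0.60 for the Shannon index, using a two-sided Wilcoxon signed-rank test, α = 0.05 and 80% power. Check: paired noncentral-t power with effective size m = n × 3/π, noncentrality d√m and m - 1 degrees of freedom.

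- n = 23, d = 0.63: m = 21.96, noncentrality 0.63 × √21.96 = 2.95, power 0.804.
- n = 25, d = 0.60: m = 23.87, noncentrality 0.60 × √23.87 = 2.93, power 0.801.

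Simulating the exact test (20,000 runs, normal differences) gives 0.800 and 0.802. The plan's figures reproduce, and nothing here changes them.

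**5. What could a reading shift do?** The documents give no Treg effect size, no SD and no size for reading bias. The following is an illustration only. It borrows the primary endpoint's test and n = 25, and assumes no true effect and normal within-person changes.

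| Assumed shift (SD of the change) | Trials rejecting at two-sided 0.05 |
|---|---|
| 0 | 4.7% |
| 0.1 | 7% |
| 0.2 | 15% |
| 0.3 | 29% |
| 0.4 | 47% |

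The shifts are assumptions. The table shows how sensitive the test would be to such a shift and is no estimate of what will happen in this trial.

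**The case against.** The strongest reply is that this is an open-label pilot whose primary endpoint is the Shannon index, that Treg is secondary, and that biased reading is inferred from the plan's silence. Several parts of that reply stand.

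- A reader might infer that 7.2.1 breaches a blinding promise in 2.4.1. The documents do not support this: 2.4.1 is a privacy statement and never undertakes to hide visit timing from the laboratory.
- A reader might infer that the label alone reveals SCFA use. It does not; it shows earlier versus later. The gap is the missing masking procedure, and the date is only one route to the time point.
- A reader might express the possible bias as a share of the 0.60 planning effect. That effect belongs to the Shannon index, and the plan gives no Treg counterpart, so the ratio would compare unlike quantities.
- A reader might want the date taken off the tubes. With ID, date and sample type as the only listed elements, the date is what separates one participant's visits on the tube. Removing it would invite mix-ups.
- The plan does not say where or by whom the blood assays are read, and section 7.2 also lists ELISA and RNA-seq, for which no reader-judgement problem is argued here.

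Open-label treatment does not, however, require open-label reading. The coding that the plan specifies leaves the time point visible, and a practical alternative exists. That makes this more than a missing detail. The storage codes in 11.3.1 do not answer it either, because nothing says that they hide visit or group.

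**Conclusion.** The concern holds for the judgement-based Treg readouts (flow-cytometry gating and suppression assays). As written, the plan lets these be read with the time point known and, for anyone with access to study data, with SCFA use known. The expected direction is stated and there is no placebo, so reading bias could enter this secondary endpoint and could not be separated from an SCFA effect.

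Its size cannot be estimated from the documents. The Shannon primary endpoint and the target of 25 evaluable participants are not shown to be affected. The conclusion assumes that readers see the study ID and date, or can reach study data, and that no unwritten masking practice exists. If one does, the plan need only state it and the point is met.

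**What to change.** 1. Keep study ID and collection date on the collection tube and in the study log.
2. Before assay or reading, have a study coordinator who does not read the assays recode aliquots and flow-cytometry files with random codes that hide participant, visit, date and group. This needs its own sample-to-visit code list, withheld from readers. The key in 11.4 links subject ID to identity and is also held by the PI and Co-PI, so it cannot serve.
3. Run each participant's stored visits in the same batch, in random order.
4. For assays run fresh, do the gating later on the recoded files with one fixed template.
5. Lock the results before the codes are opened.
6. Clarify the privacy wording in 2.4.1 so that it agrees with 5.5.2 and 7.2.1, without removing the date from collection tubes.

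The cost is a code list, rules for who holds it, and a small extra handling step. No additional assays are needed. The downsides are some risk of relabelling error, and that fresh assays are masked only at the reading stage.

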7.2.2 Specimen Shipment

If stool sample is NOT collected on day of visit (either day 0, month 1, month 2), participant can opt to collect specimen at home in a collection kit that we provide, and ship, on provided ice packs to

[name]/[name] MiCRA Lab
NYU Hospital for Joint Diseases
[name]
[name]

Specimens can be shipped Monday, Tuesday, or Wednesday with a shipping label that we provide.

7.3 Study Schedule

	Screening/Baseline	Month 1	Month 2*	Month 12*
Visit #	1	2	3*	4*
Day#	- 15 to 0	30±15	60±15	61 to 421
Informed consent	X			
Medical history	X			
Medications	X	X	X	X
MDHAQ Questionnaire	X	X	X	X
TJ/SJ counts	X	X	X	X
DAS28	X	X	X	X
Blood collection	X	X	X	X
Stool/urine sample	X	X	X	X
Dispense SCFA	X	X*		
Adverse events	X	X	X	X

***Optional**

Note: SCFA will not be dispensed for participants choosing to not take the supplement.

7.3.1 Screening/Enrollment/Baseline

Screening/Enrollment/Baseline (Visit 1, Days -15 to 0)

- Obtain informed consent of potential participant verified by signature on study informed consent form.
- Verify inclusion/exclusion criteria.
- Obtain urine pregnancy test.

- Obtain demographic information, medical history, medication history, alcohol and tobacco use history.
- Medical history and review of medications will be performed.
- DAS28 and MDHAQ questionnaire will be performed and recorded to monitor for adverse events.
- TJ/SJ counts will be measured by the physician during physical exam.
- Oral supplement will be dispensed for participants taking the supplement.
 - Oral supplement will not be dispensed for participants choosing to not take the supplement*
- Blood will be collected.
 - For each subject, approximately 5 tablespoons (75 cc) of blood will be collected in red (no anticoagulant) top, Pax gene tube for genomics, lavender (EDTA anticoagulant) top, green (heparin) and blue (sodium citrate anticoagulant) top tubes. Approximately 3 tablespoons (40 cc) of blood will be used for the different measurements of markers of inflammation and immune activation, and approximately 2 tablespoons (30 cc) of blood will be used to purify cells, RNA and DNA and then stored in -80C/liquid nitrogen for functional profiling.
 - The drawing of a maximum of 5 tablespoons (75 cc) of blood is justified by the need for the above referenced tests, measurements, and purification and to ensure that sufficient number of PBMCs, RNA and serum/plasma are present. These tubes will be drawn at the time of the standard of care blood draws for routine patient care monitoring. This amount of blood is medically safe to draw. The physician will always ensure the safety of drawing this volume of blood.
- Stool sample will be collected.
- Urine sample will be collected.
- All adverse events will be documented.

7.3.2 Intermediate Visits

Visit 2 (30 days \pm 15 days)

- Inclusion/exclusion criteria will be reviewed with participant
- DAS28 and MDHAQ questionnaire will be performed and recorded to monitor for adverse events;
- TJ/SJ counts (if arthritis is present) will be measured by the physician during physical exam
- Oral supplement will be dispensed as per above table
 - Oral supplement will not be dispensed for participants choosing to not take the supplement. *
- Review of medications will be performed;
- Blood will be collected;
- For each subject, no more than approximately 5 tablespoons (75 cc) of blood will be collected in red (no anticoagulant) top, Pax gene tube for genomics, lavender (EDTA anticoagulant) top, green (heparin) and blue (sodium citrate anticoagulant) top tubes. Approximately 3 tablespoons (40 cc) of blood will be used for the different measurements of inflammation, immune activation, and other markers, and approximately 2 tablespoons (30 cc) of blood will be used to purify cells and RNA and then stored in -80C/liquid nitrogen for functional profiling.
- Stool sample will be collected as per above table;
- Urine sample will be collected;
- Adverse events will be reviewed and recorded;
- Oral supplement adherence will be reviewed with participant and recorded.
 - Oral supplement adherence will not be reviewed with participants choosing to not take the supplement. *

7.3.3 Study Visit (optional)

Visit 3 (60 \pm 15 days)

- Inclusion/exclusion criteria will be reviewed with participant
- DAS28 and MDHAQ questionnaire will be performed and recorded to monitor for adverse events;
- TJ/SJ counts (if arthritis is present) will be measured by the physician during physical exam
- Review of medications will be performed;
- Blood will be collected;

- For each subject, no more than approximately 5 tablespoons (75 cc) of blood will be collected in red (no anticoagulant) top, Pax gene tube for genomics, lavender (EDTA anticoagulant) top, green (heparin) and blue (sodium citrate anticoagulant) top tubes. Approximately 3 tablespoons (40 cc) of blood will be used for the different measurements of inflammation, immune activation, and other markers, and approximately 2 tablespoons (30 cc) of blood will be used to purify cells and RNA and then stored in -80C/liquid nitrogen for functional profiling.
- Stool sample will be collected as per above table;
- Urine sample will be collected;
- Adverse events will be reviewed and recorded;
- Oral supplement adherence will be reviewed with participant and recorded.
 - Oral supplement adherence will not be reviewed with participants choosing to not take the supplement. *

7.3.4 Additional Optional Study Visit

Visit 4 (Up to 12 Months After Final Visit)

- Inclusion/exclusion criteria will be reviewed with participant
- DAS28 and MDHAQ questionnaire will be performed and recorded to monitor for adverse events;
- TJ/SJ counts (if arthritis is present) will be measured by the physician during physical exam
- Review of medications will be performed;
- Blood will be collected;
- For each subject, no more than approximately 5 tablespoons (75 cc) of blood will be collected in red (no anticoagulant) top, Pax gene tube for genomics, lavender (EDTA anticoagulant) top, green (heparin) and blue (sodium citrate anticoagulant) top tubes. Approximately 3 tablespoons (40 cc) of blood will be used for the different measurements of inflammation, immune activation, and other markers, and approximately 2 tablespoons (30 cc) of blood will be used to purify cells and RNA and then stored in -80C/liquid nitrogen for functional profiling.
- Stool sample will be collected as per above table;
- Urine sample will be collected;
- Adverse events will be reviewed and recorded;

7.3.5 Withdrawal/Early Termination Visit

If participant withdraws or if early termination occurs a final blood draw and stool and urine collection, medication list, MDHAQ, TJ/SJ count should be obtained, provided that the participant is willing.

7.3.6 Unscheduled Visit

Treating physician will examine participant and make any necessary medication adjustments as per his/her discretion. Study team will note medication history, TJ/SJ count and discuss oral supplement adherence with participant as necessary. All data collected will be documented as a separate entry in REDCAP.

7.4 Concomitant Medications, Treatments, and Procedures

All concomitant prescription medications taken during study participation will be recorded on the case report forms (CRFs). For this protocol, a prescription medication is defined as a medication that can be prescribed only by a properly authorized/licensed clinician. Medications to be reported in the CRF are concomitant prescription medications, over-the-counter medications, and non-prescription medications.

